59 Regardless of amount of prenatal education provided, Southview Medical Center will study
 60 participating patients at the time of admission for delivery who watch an 8 minutes
 61 second patient education DVD titled "Jumping into Kangaroo Care" by the Ohio Department
 62 of Health. Of importance, studies so far have shown no clear pattern for the outcome of
 63 breastfeeding in respect to intervention timing (7). In an analysis regarding video modeling,
 64 patients who viewed videotapes regarding treatment options had a greater understanding of
 65 the risks and benefits of those choices and were more apt to be active participants in
 66 decision making (11). Audio-visual material can also be entertaining and can be used by
 67 those who have limited literacy. Moreover, the information provided to patients on video has
 68 the advantage of being repeatable and consistent, which would allow us to provide the same
 69 information to all of our patients (12). By educating our patients in a video format at the
 70 beginning of their delivery admission, patients will have time to formulate questions and
 71 opinions to help them engage in an active dialogue with the staff that will be performing the
 72 delivery. The goal of educating mothers is not only to increase their knowledge and skills
 73 but also to influence their attitudes (13). By providing a video which models SSC to all non-
 74 emergent anticipated vaginal deliveries upon admission to the hospital, our hope is to
 75 encourage patients to actively participate in SSC at the time of delivery and become their
 76 own advocates.

77

78 The main purpose of this study is to determine the effect of prenatal video education on
 79 pregnant women's intention to practice SSC after birth. This study is critical for our hospital
 80 as quality measures for Southview Medical Center for quarter one of 2017 showed that we
 81 have only been 50% successful at initiating skin to skin in vaginal deliveries after 37 weeks
 82 gestation with a 5 minute APGAR of 7. Our goal as a hospital per BFHI is 82%. Our
 83 hypothesis is that 30% or more women who did not plan to use SCC would indicate their
 84 intention to use SSC post-intervention as compared to those who did not receive the
 85 intervention.

86 **Human Subject Population**

87 **Method of Subject Identification**

88 Patients will be recruited and consented to participate in the study at the time of admission

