- 133 • Unstable medical status
- 134 • Expecting an unstable baby requiring medical resuscitation
- 135 • Under the age of 18
- 136 • Non-English speaking requiring translation services

137 **Vulnerable Subjects**

138 Pregnant women may be considered vulnerable subjects. Teach back method during the
139 consent process will be used to ensure understanding regarding participation. This study
140 poses no medical risks to pregnant women, fetuses, or neonates. Any pregnant woman
141 appearing to be in a cognitive or emotional state that would prevent informed consent would
142 be excluded.

143 **Research Design and Methods**

144 If participating in the study in the experimental group the patient would watch the video prior to
145 delivery.

146
147 A sample size of 240 (120+120) will participate in this randomized control trial. Alternate
148 patients will be randomized at the time of admission into no video (Group A) and video groups
149 (Group B). 120 patients will be in Group A. 120 patients will be in Group B.

150
151 Randomization will occur in the order that they get enrolled into the study. If an eligible patient
152 wishes to participate in the study, the resident obtaining consent will consult the list of patients
153 to determine if that particular patient will be in Group A or Group B. The first patient enrolled
154 would be in Group A and asked a pre-survey regarding:

- 155 • their intention to practice skin to skin at the time of delivery
- 156 • if they participated in skin to skin in a previous pregnancy
- 157 • if they had any formal education about skin to skin
- 158 • if they did have formal education was it either
 - 159 ○ a.) Provided at a prenatal appointment,
 - 160 ○ b.) A formal class led by either a nurse or a lactation consultant.

161 The second patient enrolled would be in Group B and take the same pre-survey, immediately
162 watch “Jumping into Kangaroo Care”, and then immediately take the post survey which would
163 ask if they intended to practice skin to skin at the time of delivery. The third patient enrolled
164 would take only the pre-survey and be in Group A, etc.

165
166 The video the patients will watch is titled “Jumping into Kangaroo Care” by the Ohio Department
167 of Health. The video is 8 minutes and 52 seconds in length. The video discusses the benefits
168 and logistics of Kangaroo Care from professional’s perspectives and from new mother’s

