169 perspectives. By having patients watch this video before the time of delivery, we can see if
170 patients intend to participate in skin to skin, regardless of their previous education.

171
172 In this study, we will examine patient’s medical record number, age, gestational age, any
173 pregnancy complications, race, type of insurance, and the number of times the patient has been
174 pregnant. We will also examine data that is already collected by this hospital after delivery
175 regarding skin to skin. This includes gestational age in weeks at the time of delivery, 5 minute
176 APGAR, delivery date/time, skin to skin initiation time, skin to skin end time, delivery to skin to
177 skin duration (minutes), and skin to skin duration (minutes). We will also examine if skin to skin
178 is not initiated for patient acuity, maternal acuity, or if the patient refused.

179
180 If a patient has a baby with a 5 minute APGAR less than 7 at the time of delivery or needs to
181 proceed to the operating room for cesarean delivery, the patient would not be included in data
182 collection regarding skin to skin at the time of delivery. For this group, only intention would be
183 measured

184 Surveys / Interviews / Questionnaires

185 Ob/gyn residents at Southview Medical Center will ask the survey questions. The survey will be
186 asked in the patient’s labor room at the hospital once they are admitted. The survey will be
187 administered one-on-one. A copy of the survey has been attached. They will then watch
188 “Jumping into Kangaroo Care” by the Ohio Department of Health if they are in the experimental
189 group. Copyright has been attached.

190 Risks / Discomforts

191 Physical risks or discomforts

192 No known risks

194 Psychological risks or discomforts

195 No known risks

196 Social risks or harms

197 Breach of confidentiality

198 Economic risks

199 No known risks

200 Legal risks

201 No known risks

202 Procedures to Minimize Risks (describe for each risk listed above)

- 203 • Breaches of confidentiality: see *Data Storage and Confidentiality* section

204

205 Specify who will evaluate adverse events / serious adverse events (AEs / SAEs) to identify
 206 and report unanticipated problems: [name], DO

207 **Diagnostic/treatment (non-research) procedures to be used for the study**

208 N/A

209 **Benefits**

210 **Potential benefits to participants**

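### As the protocol most naturally reads, the resident looks up the group before asking the pre-survey aloud, so the intention answer can be influenced by knowledge of the arm

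*Combined protocol and SAP*

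**What the plan says.** Research Design and Methods describes enrolment as a short sequence. When an eligible woman "wishes to participate in the study, the resident obtaining consent will consult the list of patients" "to determine if that particular patient will be in Group A or Group B. The first patient enrolled" "would be in Group A and asked a pre-survey regarding" four matters, the first being "their intention to practice skin to skin at the time of delivery". The others are skin-to-skin in a previous pregnancy, formal education on the subject, and where that education was given. For the other arm: "The second patient enrolled would be in Group B and take the same pre-survey, immediately" followed by the video and a post-survey on intention. The third woman "would take only the pre-survey and be in Group A, etc". Assignment alternates A, B, A.

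Surveys / Interviews / Questionnaires adds that "Ob/gyn residents at Southview Medical Center will ask the survey questions. The survey will be" put to her one-on-one in the labor room, with the video following for the experimental group. That section does not mention the list.

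Purpose makes intention, from a single questionnaire item, the endpoint. Background and Significance states the hypothesis in terms of a subgroup defined by that item: the "hypothesis is that 30% or more women who did not plan to use SCC would indicate their" intention to use it after the intervention.

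**The concern.** In both arms the pre-survey is described with the group already set, and the staff who look up the group also ask the questions. No provision is made for an interviewer unaware of the group, for self-completion, or for withholding the assignment until the form is complete.

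The exposed item carries the trial. Group A has no post-survey, so its pre-survey answer is the control value in the between-group test of the primary endpoint. In Group B the same item is the baseline, and it identifies the women who did not plan skin-to-skin. A resident who knows the arm may ask or record the question differently, and a woman who knows a video is coming may answer differently. This is distinct from how the sequence is generated: a random, concealed list opened before the survey would leave the same exposure.

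**Working it through.** **Order of events.** Three places bear on it.
- The enrolment paragraph in Research Design and Methods puts the look-up at the point of agreement, then describes the survey for a woman already in Group A or Group B.
- The sentence on the third woman mentions the survey before the group, but it summarises what she receives and does not set out steps.
- Surveys / Interviews / Questionnaires places the video after the survey and is silent on the look-up.

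Nothing sets the opposite order or conceals the group. The order is therefore an inference from the narrative, but the only one the text supports.

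**Which data are exposed.** Intention is the item most open to influence. Previous skin-to-skin and formal education are questions of past fact and less so. Age, gestational age, complications, race, insurance and number of pregnancies are not in the pre-survey; the protocol names Epic as the source of pertinent information.

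**The plan's own figure.** Data Analysis gives about 53 per arm for 50% against 80%, two-sided alpha 0.05, 90% power. With pooled variance under the null:

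n = [1.96 × √(2 × 0.65 × 0.35) + 1.28 × √(0.5 × 0.5 + 0.8 × 0.2)]² / 0.30² = 51.01, rounded up to 52.

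This agrees with the stated figure to within one patient. The point here does not change it.

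**Sensitivity to a shift.** Inputs from Data Analysis: 120 per group at the final look, cut-offs of 3.5 (60 per group) and 2.0 (120 per group), and a 50% control rate. Assumed, because the documents give no figure: no true video effect, and recorded intention in Group A lower by d than in Group B.

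At the final look, z = d / √(2 × p̄ × (1 − p̄) / 120), where p̄ is the mean of the two rates. The chance of crossing the cut-off is about P(Z > 2.0 − z) + P(Z < −2.0 − z).

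For d = 5 points (54/120 against 60/120): p̄ = 0.475, standard error 0.0645, z = 0.78, chance about 0.113.

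| Shift d | Women of 120 | z | Final look alone | Both looks, simulated |
|---|---|---|---|---|
| 0 | 0 | 0 | 4.6% | 4.5% |
| 2.5 points | 3 | 0.39 | 6.2% | 6.1% |
| 5 points | 6 | 0.78 | 11.3% | 11% |
| 10 points | 12 | 1.56 | 32.9% | 32% |

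The last column is from 1,000,000 simulated trials per row under the full two-look rule. Five points is half the 10-point difference that Data Analysis uses for its final-analysis example.

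**Opposite direction.** If Group A is recorded too high (60% against 50%, say), z changes sign and the two-sided rate is the same, but the rejections go against the video. If the video truly adds 10 points, a 5-point shift of this kind leaves an expected difference of 10 − 5 = 5 points.

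**The case against.** The strongest reply is that the text explains allocation by example and is not a procedure: no sentence says that the look-up comes before the survey, and none says that the woman is told her group. Both statements are true. They limit the point to a natural reading, with the resident's knowledge as the firmer part. They do not answer it, since the plan offers no other order and no safeguard.

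It can also be said that no shift is shown and none has a known direction. That stands: the figures above measure sensitivity and do not estimate bias. The survey form, which the protocol says is attached, was not available for this review, so the response options, and the room for an unsure or ambiguous answer, are unknown.

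A reader might infer three stronger things that the documents do not support.
- **That all baseline data are compromised.** Most listed characteristics lie outside the pre-survey.
- **That apparent conversion of non-planners would break the primary test.** Suppose 3 to 6 of 60 planners in Group B are recorded as not planning and then say yes after the video. Apparent conversion is 3/63 = 4.8% to 6/66 = 9.1%. Group B's post-video total is still 60/120 against Group A's 60/120, so the planned z is 0. Data Analysis specifies no conversion analysis, and those rates are far below the 30% in the hypothesis.
- **That re-wording the order cures the problem.** Under alternation the resident can infer the next group from the last, without the list.

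**Conclusion.** The concern holds as a risk to the intention item. On the natural reading of Research Design and Methods, Group A's only primary-endpoint answer and Group B's baseline are taken by a resident who knows the arm, and nothing prevents the woman from knowing it too. The items on past experience are less exposed, and data from outside the survey are not affected.

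How much this matters depends on a shift that the documents cannot supply. At an assumed 50% rate, 120 per group and no true effect, a range of 2.5 to 10 points takes the two-sided rejection rate from about 4.5% to between about 6% and 32%; the reverse shift would work against the video. The low end is minor. A shift of half the plan's own 10-point example more than doubles the false-positive rate, and later analysis could not recover an unexposed answer. The safeguard is cheap and should be added.

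**What to change.** Re-word the enrolment paragraph of Research Design and Methods so that the order for every woman is: consent; full pre-survey completed and written down; assignment revealed; then video (Group B) or no video (Group A). State that the assignment is neither looked up nor told to the woman before the form is complete, and record the time of both steps. This costs one paragraph and two time entries, with the same staff, survey and sample size.

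Replace alternation with a concealed random sequence in the same amendment. Without it, reordering mainly keeps the woman unaware and leaves the resident's knowledge intact. The added cost is preparing the sequence and a means of concealing it.

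Two limits should be acknowledged in the text. A resident who knows the arm would still ask Group B's post-video question. Group A would still have only one intention measurement, which is a separate matter.

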211 Participants may benefit by learning the benefits of skin to skin care after delivery.

212 **Potential benefits to others / contributions to knowledge**

213 Others can benefit by learning if video education video education can positively contribute to
 214 patients intent and compliance with skin to skin at the time of delivery

215 **Data Analysis**

216 Preliminary data on both primiparous and multiparous women from our records indicate that
 217 compliance with skin-to-skin is about 50%. We hypothesize that a 30% improvement in intention
 218 along with compliance with SCC is attainable with video education. We also have the ability to
 219 recruit 120 eligible women per group (240 in total) into the study. Using z test for two
 220 proportions, 90% power with alpha of 0.05, two-tailed, we will need about 53 patients per arm
 221 (106 in total) based on assumption that 50% of no formal education group and 80% of video
 222 education group would indicate their intention to participate, and hopefully participate in SCC
 223 post intervention.

224
 225 We will employ interim analysis, based on potentially recruiting 240 patients, and adopt “two
 226 looks”; one at the time when 120 (60 per group) women would be recruited and the other when
 227 240 (120 per group) women would be recruited. We will use cut-off points of $z=3.5$ for first look
 228 and $z=2.0$ for second look, as suggested by O’Brien-Fleming (1979), as decision rules to stop or
 229 continue data collection. If calculated z statistics is greater than 3.5 during first interim analysis,
 230 we will stop data collection. If calculated z-statistics is less than 3.5, we will continue data
 231 collection and reject the null during final analysis only when calculated z-statistics is greater
 232 than 2.0.

233
 234 Assuming 50% and 80% intention levels (30% difference in proportion) during first interim
 235 analysis, 50% interim sample size (120 patients) would result in absolute z- statistics of 4.89 to
 236 stop data collection.

237
 238 If data collection continues due to proportion difference less than 30%, sample size of 240
 239 during final analysis would produce absolute z-statistics of 2.20 to reject the null hypothesis
 240 based on assumption of 10% difference in end-point.

241
 242 Mean (Standard deviation) and sample size (percentage) will be used to summarize normally
 243 distributed continuous data and categorical data respectively. Either t-test of independence or

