 244 Chi-square test of independence will be used to test if significant differences exist between two
 245 groups on quantitative data or on categorical data respectively, at alpha of 0.05, two tailed. Z-
 246 test of two proportions would be used to test if significant differences exist between two groups.

247 Logistic regression would be used in order to account for other variables if necessary. SPSS
248 version 22 will be used to analyze data. [name], associated with Ohio University, will act as our
249 statistician and help us to analyze our data.

250 Data Monitoring to Ensure Safety of Subjects

251

252 Check if this study involves treatment or intervention and provide narrative of plan to
253 monitor data to ensure safety of subjects below:

254 The video intervention involves minimal risk.

255 Privacy Protections

256 We will collect coded data to ensure patient's privacy. We will also recruit and consent in
257 patient's private rooms on labor and delivery.

258 Data Storage and Confidentiality

259 Check all of the following which will be used to access (review), collect, receive, and/or
260 transmit study information:

- 261 **Email** **Camera/Camera Phone** **Portable media (flash drive, CD/DVD, hard drive, etc.)**
262 **Laptop** **Wireless Device** **Internet data access/data entry**
263 **Paper** **KHN Workstation** **Non-KHN computer**
264 **Other (specify):** [Click here to enter text.](#)

265 Describe where data/ records/ samples will be stored and how they will be kept secure:
266 Data will be stored in two binders on labor and delivery at the resident work station. Only
267 approved ob/gyn residents will have access to the study binders. One binder will have the
268 patient's name and enumber along with a number assigned to each patient. The other
269 binder will have the surveys with each survey having the number assigned to each patient.

270
271 Any email communication with PHI will be KHN only. If outside KHN email is needed it will
272 be encrypted. Internet data access will be through Epic. All electronic records will be stored
273 on the resident KHN workstation on L&D that is password protected and only accessible by
274 the PI.

275 Specify who will have access to study information/ to whom it will be released (if applicable):
276 Ob/gyn residents approved to participate in this study will have access to the study
277 information as they will help with the data collection

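### A t-test on time to skin-to-skin contact and its duration would compare only women who started, a group selected after allocation by the behaviour the video targets; the named endpoints are not affected

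*Combined protocol and SAP*

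**What the plan says.** The Purpose section names two endpoints, both binary: intention to practise skin-to-skin contact, and contact within five minutes of delivery.

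Research Design and Methods then lists hospital data to be examined after delivery. The list includes "APGAR, delivery date/time, skin to skin initiation time, skin to skin end time, delivery to skin to" and ends with "skin duration (minutes), and skin to skin duration (minutes". The first of those two durations is the interval from delivery to contact; the second is the length of contact. The same paragraph foresees women who never start, because it records whether contact "is not initiated for patient acuity, maternal acuity, or if the patient refused". The next paragraph removes a different set of women from the skin-to-skin data, those with a low APGAR or a caesarean delivery ("If a patient has a baby with a 5 minute APGAR less than 7 at the time of delivery or needs to" proceed to theatre).

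Data Analysis gives one general rule for group comparisons: "distributed continuous data and categorical data respectively. Either t-test of independence or" "Chi-square test of independence will be used to test if significant differences exist between two" "groups on quantitative data or on categorical data respectively, at alpha of 0.05, two tailed". It names no variable. Nowhere do the documents say whether a woman who did not start counts as zero, takes a worst rank, is censored or is left out.

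On rates, Data Analysis reports from hospital records that "compliance with skin-to-skin is about 50" percent, and hypothesises a 30-point improvement in intention together with compliance.

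**The concern.** A woman with an eligible vaginal birth who refuses, or in whom acuity prevents contact, has no initiation time and no interval from delivery. If her fields are blank, a t-test drops her without comment. What remains is Group B starters against Group A starters. Whether a woman starts is settled after allocation and is the behaviour the video is meant to change, so the two sets of starters are not protected by the allocation. The more women the video persuades, the larger the share of Group B starters with no counterpart in Group A.

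These are the only graded measures of actual practice in the plan. A starters-only test could report a video that brings more women to skin-to-skin contact as delaying or shortening it, or could flatter the video. It could also show nothing when the gain lies wholly in the number who start. The APGAR and caesarean exclusion does not solve this, because refusals and other non-starts remain among the eligible vaginal births.

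**Working it through.** **Inputs from the documents.** 120 women per arm; 50% in the control group and 80% in the video group; two-sided alpha 0.05. The plan's sample size rests on these two rates and reproduces closely: n = [1.96·√(2·0.65·0.35) + 1.28·√(0.5·0.5 + 0.8·0.2)]² / 0.3² gives 52 per arm after rounding up, against about 53 stated.

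**Assumptions.** The 50% and 80% are taken as shares who ever start. The video puts no woman off. The documents give no minutes for time to start or duration, so every minute below is assumed.

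**Step 1: who is compared.** Before the APGAR and caesarean exclusions, control starters number 120 × 0.5 = 60 and video starters 120 × 0.8 = 96. The share of video starters who started only because of the video is (pV − pC)/pV = (0.8 − 0.5)/0.8 = 37.5%, or 36 of 96. With a video rate of 70% the share is 28.6%, and with 60% it is 16.7%.

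**Step 2: the bias.** If the video does not alter the women who would start anyway, the starters-only difference in means equals that share × (mean in induced starters − mean in usual starters). With induced starters assumed 5 min later and 30 min shorter:
- time: 0.375 × 5 = +1.9 min
- duration: 0.375 × (−30) = −11.3 min

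**Step 3: the sign can reverse.** Take 60 min in usual starters and 30 min in induced starters. Mean duration among video starters is 60 − 11.25 = 48.75 min, against 60 among control starters, so about 11 min less. Counting non-starters as 0, the means per woman are 0.8 × 48.75 = 39 and 0.5 × 60 = 30, so 9 min more.

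**Step 4: how often the t-test would be significant.** Simulation at 50% against 80%, 120 per arm, 4,000 trials. Usual starters: 5 min (SD 5) to start, 60 min (SD 30) duration.

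| Induced starters | Difference, time / duration | Significant against the video, time / duration | Significant for the video, time / duration |
|---|---|---|---|
| same as usual | 0 / 0 min | about 2% / 2% | about 2% / 3% |
| 3 min later, 15 min shorter | +1.1 / −5.6 min | 27% / 20% | about 0% / 0% |
| 5 min later, 30 min shorter | +1.9 / −11.3 min | 57% / 57% | about 0% / 0% |
| 3 min earlier, 15 min longer | −1.1 / +5.5 min | about 0% / 0% | 27% / 19% |

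**Step 5: a smaller contrast with different distributions.** 60% against 80% start; 102 analysable women per arm (15% of 120 assumed excluded); exponential times and gamma durations; usual starters 4 min and 60 min. The induced share is 0.2/0.8 = 25%.

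| Induced starters | Expected shift, time / duration | Significant against the video, time / duration |
|---|---|---|
| 12 min, 30 min | 0.25 × 8 = +2.0 / 0.25 × (−30) = −7.5 min | about 45% / 32% |
| 8 min, 30 min | +1.0 / −7.5 min | about 19% / 32% |
| 5 min, 50 min | +0.25 / −2.5 min | about 5% / 8% |
| same as usual | 0 / 0 min | about 2% / 2% |

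If the video also moves usual starters from 4 to 3 min and from 60 to 66 min, the first row falls to about 15% and 7%.

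**Step 6: alternatives in the Step 5 setting.** A two-proportion test of started or not detects the benefit in about 88% of trials in every row. A Mann-Whitney test on all women (non-starters at worst rank for time, 0 for duration) detects it in about 71% when induced starters resemble usual ones, and in about 42% (time) and 34% (duration) in the 12 min, 30 min case.

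**The case against.** The strongest reply is that the plan never commits to this test. The two durations are not named endpoints. They sit in a list of routine hospital data beside gestational age and APGAR, and the clock times are needed anyway to derive the five-minute endpoint. The t-test rule is generic and would serve equally well for maternal age. How a non-starter's duration is coded is not stated; it could already be zero. Non-starters stay visible through the recorded reasons and can count as failures on the five-minute endpoint. The direction of any bias is assumed, and a comparison of proportions started has more power than a rank test.

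Most of this stands, and it sets the severity. It does not remove the point. The general rule is the only one the plan offers for quantitative data, these two measures are quantitative, and time to initiation cannot exist for a woman who never started. Applied as written to recorded values, the rule gives a comparison that allocation does not protect.

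A reader might go further and infer that the plan prespecifies a starters-only test of two outcomes, or that the starters are self-selected. The documents support neither. The test reaches these measures only through the general rule, and acuity as well as refusal can prevent a start, so selected after allocation is the accurate description.

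**Conclusion.** The point holds as a lower-severity improvement to supporting measures. The selection follows from the plan's own rates, if these are read as shares who ever start: 37.5% of video-arm starters would have no counterpart among control starters.

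The direction and size of the bias do not follow from the documents. The video looks later and shorter if induced starters begin later or hold for less time, and looks better than it is if they do the opposite. If they are like the others, the test shows nothing although more women start. At 60% against 80%, wrong-direction significance ran from about 5% to 45% over the assumed scenarios in which induced starters were later and shorter. At 50% against 80% with other assumed minutes it reached 57%.

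It may be tempting to conclude that the video will appear harmful, or that the trial's main conclusions are at risk. The documents support neither. They say nothing about how persuaded women differ, and both named endpoints are binary and do not use these means.

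**What to change.** In Data Analysis, state that the interval from delivery to skin-to-skin contact and the duration of contact are exempt from the general t-test rule. Report starters-only means as description, without a test, beside the number and proportion who started in each group.

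If the groups are to be tested on these measures, include every woman in the practice analysis. Set duration to 0 and give time to initiation the worst rank for women who did not start, and compare the groups with the Mann-Whitney test.

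The cost is a sentence or two and no new data, because non-initiation is already recorded. The small downside of the rank test is that it gives a rank comparison rather than a mean difference in minutes. It also partly repeats the comparison of proportions started, with less power.
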